#### ***mLCI interferometer***

The centerpiece of LCI instrumentation is an interferometer, in which light from a known reference distance is combined with light returning from the probe. In our multiplexed design, 6 channels are simultaneously illuminated and interfered with each of 6 independent references. The mLCI thus contains 6 complete fiber optic interferometers, and fiber-optic switches redirect the optical inputs and outputs to progress through the 36 channels in a sequence of 6 acquisitions.

The 6 interferometers in the mLCI system are connected individually to each of 6 parallel fiber-optic spectrometers (Avantes, Broomfield, CO), which interface with the computer via one common USB connection.

The light source from the mLCI system is a superluminescent diode (Superlum, Moscow, Russia) emitting infrared light at wavelengths between 815 and 845 nm. The total output power of the SLD at its output aperture is less than 25 mW, but the amount of power delivered by the probe is far less. The power at each of the individual 36 foci at the probe output is less than 500  $\mu$ W (0.5 mW).

The maximum permissible exposure (MPE) for exposures greater than 10 seconds on skin is 3.6 mW/mm^2 at our principal wavelength of 830 nm (ANSI Z136.1). In our system, only 6 channels are simultaneously illuminated. Our imaging region in the tissue is 16 mm (defined by the length of our row of 6 spots) x 3.5 mm (defined by the minimum limiting aperture given in ANSI Z136.1) = 56 mm^2. Our total permissible power is thus 3.6 mW/mm^2 x 56 mm^2 = 201 mW. The totality of our 6 foci = 6 x 0.5 mW = 3 mW, which is far short of the ANSI MPE.

#### ***White light imaging module***

A white light imaging module is configured to provide video endoscopy guidance for the probe placement on the cervix. This module consists of a white light LED optically coupled to an illumination fiber that is enclosed in the probe, as well as an imaging

camera and relay optics to digitize the endoscopic image from the probe's white light fiber bundle.

### **Computer**

A laptop computer (Lenovo, Beijing, China) performs the data acquisition and control through a custom application in Labview (National Instruments, Austin, TX). Real-time display of the white-light endoscopic images is provided, as well as synchronized acquisition of LCI data from spectrometers. Through a customized microcontroller module, this software also implements control of reference mirror positions by stepper motor and control of fiber-optic switch positions.

### **Physical enclosure**

The mLCI interferometer, white light imaging module, and computer are situated upon a wheeled steel cart. The fiber-optic interferometer components are protected by a metal enclosure. Power to all components is provided through standard 120V mains routed through an uninterruptible power supply (UPS), which allows temporary disconnection of AC power for system transportation or due to accidental action without interrupting the operating state of the mLCI system.

### **Study Procedures for subjects at Duke**

Each subject will attend 1 study visit that will last between 1 – 1.5 hours and include the following procedures.

- Read consent form
- Ask / answer questions
- Sign consent form
- Complete brief medical questionnaire to determine eligibility
- Urine pregnancy test – must be negative before imaging can occur
- mLCI examination of the cervix (without speculum)
- mLCI examination of the cervix (with speculum)

We will obtain written informed consent and confirm eligibility criteria. Data collection will include a brief medical history and pregnancy testing. Participants will be interviewed one-on-one to complete the questionnaire regarding medical and reproductive history. The nurse or doctor will then perform the mLCI study measurements.

The nurse or doctor will gently place the mLCI probe against the cervix. Lubricant will be placed on the outside of the probe for subject comfort. White light camera visualization, incorporated into the mLCI probe, will guide the probe positioning by the clinician to confirm contact with the cervical epithelium. Up to 4 minutes will be allotted for probe manipulation for optimal contact. The probe will then be held in place for mLCI data acquisition for up to 1 minute. When data collection is completed, or permitted time is elapsed, the mLCI probe will be removed and placed on a custom holder that prevents the contact portions of the probe from coming into contact with contaminating surfaces.

The nurse or doctor will then insert a speculum in order to directly visualize the cervix. The mLCI probe will again be placed against the cervix with 4 minutes allotted for probe manipulation and 1 minute for mLCI measurements.

If manipulation of the probe with the aid of a speculum does not allow satisfactory placement on the cervix for mLCI imaging within the permitted time, an additional attempt may be made with an alternate speculum, such as a Pedersen Open-Sided speculum, if

the medical practitioner performing the procedure believes the alternate speculum to be more likely to result in correct probe placement. If the alternate speculum is used, then an additional 4 minutes will be allotted for probe manipulation with the alternate speculum, and 1 minute for mLCI measurements. The timing of each phase of the procedure is summarized in the following table.

**Table 1:** Maximum allotted times of mLCI probe insertion

Insertion method	Criteria	Time for probe placement	Time for mLCI acquisition	Maximum total time
Without speculum	All patients	4 min	1 min	5 min
With standard speculum	All patients	4 min	1 min	5 min
With alternate speculum	Optional (only if standard speculum not satisfactory AND practitioner believes alternate may achieve better result)	4 min	1 min	5 min

Comparing measurements made by inserting the mLCI device with and without a speculum will allow us to determine if the white light visualization by the camera is sufficient to correctly place the probe over the cervix without having to use a speculum in future studies. The ability to use an alternate in the event that a conventional speculum does not permit adequate mLCI probe placement will also inform our selection of the type of speculum, if any, that is most suited for subsequent studies.

### **Study Procedures for subjects at Jacobi**

Subjects will be informed of the study when they present to the clinic for a regular clinical care visit. If interested in participating, subjects will complete the following study-related procedures in addition to the standard of care visit procedures.

- Read consent form
- Ask / answer questions
- Sign consent form
- Urine pregnancy test – must be negative before imaging can occur
- Colpophotography of cervix to compare with mLCI data
- mLCI examination of the cervix (with speculum)

We will obtain written informed consent and confirm eligibility criteria. Data collection will include a brief medical history and pregnancy testing.

The doctor will then insert a speculum in order to directly visualize the cervix. Colpophotographs will be taken to compare to mLCI data during data analysis. The doctor will then gently place the mLCI probe against the cervix. White light camera visualization, incorporated into the mLCI probe, will guide the probe positioning by the clinician to confirm contact with the cervical epithelium. The probe will then be held in place for mLCI data acquisition for up to 1 minute. When data collection is completed, the mLCI probe will be removed and placed on a custom holder that prevents the contact portions of the probe from coming into contact with contaminating surfaces.

The doctor will then continue with the rest of the patient's standard of care visit procedures.

At some visits, the physician may choose to make an additional measurement with the mLCI device, by inserting it without a speculum and using the white light camera (incorporated into the mLCI probe) for visual guidance to position the probe. Comparing measurements made by inserting the mLCI device with and without a speculum will allow us to determine if the white light visualization by the camera is sufficient to correctly place the probe over the cervix without having to use a speculum in future studies.

### **Selection of Subjects at Duke**

This project will recruit healthy women who:

- are able to provide informed consent
- are at least 21 years old
- are willing to abstain from sexual intercourse for at least 24 hours before the study visit

Participants meeting any of the following exclusion criteria will be excluded from taking part in this study. Women must not:

- be pregnant
- have given birth to a baby
- have a current gynecologic infection or discharge
- be using an IUD
- have had any cervical surgery
- have had medical or cosmetic surgery involving the reproductive organs or genitals within the past 6 months
- be currently enrolled in any research studies involving the application of vaginal formulations
- be employed or supervised by the study investigators
- have any other condition that, in the opinion of the study clinician, would contraindicate participation in the study

### **Selection of Subjects at Jacobi**

We do not have any role in selection of the research subjects at Jacobi: this is the responsibility of that site.

### **Subject Recruitment & Compensation at Duke**

We will recruit up to 15 women to enroll in this study, in order to achieve the target number of 10 subjects who complete the study.

The study will be advertised on the ResearchMatch website. Recruiting will be managed by our study coordinator. The inclusion of minorities in the group of women recruited will reflect the local distribution in the Durham area.

After learning about the study, prospective subjects will call the study coordinator for more information. During this telephone call, the study coordinator will state the study requirements plus a brief description of the procedures. If the prospective subject is interested in participating in the study, a study visit will be scheduled. The prospective subject's contact information will be kept in a locked desk or file cabinet or password protected file in the study coordinator's office. If the prospective subject states that she does not qualify or is not interested in participating, the contact information will be destroyed.

Subjects will be compensated \$50 per visit (1 visit per subject).

### **Subject Recruitment & Compensation at Jacobi**

We do not have any role in recruiting or compensating research subjects at Jacobi: this is the responsibility of that site.

### **Consent Process at Duke**

The consent process will be conducted by the study coordinator at a meeting in the study coordinator's office or other suitable private location (PI's office, conference room, clinic consult room).

Thirty minutes will be allocated for conducting the initial consent discussion, allowing time for the prospective subject to read the consent form and ask any questions she may have. At the consenting interview, the study coordinator will:

- explain the study procedures in detail, including risks and compensation
- inform the participant of her rights as a research subject, including the right to withdraw at any time
- give the participant a chance to ask any questions she may have

The prospective subject may then sign and date the consent form if she chooses to participate at that time. She may take more time to consider her decision and sign the consent form at a later date if she chooses. The prospective subject will have as much time as she needs to decide whether or not to participate. However, enrollment will continue, and if all study slots are full by the time the prospective subject decides to participate, she may not be enrolled in the study. Once the consent form is read and signed, the subject and study coordinator will complete the Informed Consent Review Check Sheet to document the consent process.

The prospective subject will then complete a brief screening questionnaire and a urine pregnancy test. Results from the screening questionnaire and pregnancy test will be reviewed to determine if the subject is eligible to continue participation in the study. If the screening test indicates pregnancy, the participant will be excused from the study and advised to follow up with her physician. Subjects who pass screening will be enrolled in the study on a first-come, first-served basis.

The prospective subject may ask questions at any time by calling the study coordinator or PI. The study coordinator will conduct all consent discussions and study visits and will be available to answer any questions that arise at those times.

To minimize the possibility of coercion or undue influence, study personnel will inform subjects of their rights as a research participant, including their right to refuse to participate or to withdraw from the study at any time without penalty. Reimbursement (\$50 per session) is not believed to be coercive, based on the time required and the nature of the research. The amount of reimbursement is comparable to similar studies. Duke students and employees under direct supervision of the study staff will not be allowed to participate in this study.

Since recruiting materials (website postings) are in written English, it is expected that anyone who calls to inquire about participating in the study will be able to read English. No provisions are in place for potential participants who do not understand English.

### **Consent Process at Jacobi**

We do not have any role in consenting subjects at Jacobi: this is the responsibility of that site.

### **Subject's Capacity to Give Legally Effective Consent at Duke**

Subjects who do not have the capacity to give legally effective consent will not be included in this study.

### **Subject's Capacity to Give Legally Effective Consent at Jacobi**

We do not have any role in assessing subjects' capacity to give legally informed consent at Jacobi: this is the responsibility of that site.

### **Study Interventions**

See above.

### **Risk/Benefit Assessment of the study in general**

#### ***Potential Risks***

Potential risks include:

1. breach of confidentiality
2. coercion
3. discomfort with the nature of the research
4. side effect from study procedures and/or devices

#### ***Potential Benefits***

There is no direct benefit to subjects participating in this research study. However, the novel mLCI device to be developed in this proposal would potentially advance the management of cervical dysplasia by assisting clinical decision-making without relying on gross colposcopic impression. The current proposal is to conduct the early feasibility studies necessary for technology development. Data will also be collected about epithelial characteristics as visualized by mLCI, which could improve our understanding about the basic biology of the cervical epithelium. The long-term goal is to develop devices that could be incorporated into routine clinical care. The mLCI device could provide real-time information to the clinician and reduce the number of clinical visits needed.

#### ***Alternative Treatments***

There are no alternative treatments to participating in this research. It is not intended to be therapeutic, but to acquire basic scientific knowledge.

### **Risk Assessment and Risk Minimization for Study Activities at Duke**

#### ***Potential Risks***

Potential risks include:

- (1) breach of confidentiality
- (2) coercion
- (3) discomfort with the nature of the research
- (4) side effects from study procedures and/or devices

#### ***Breach of Confidentiality***

Subjects will provide personal information, including sexual history and health information. Breach of confidentiality will be avoided by training research staff in the protection of human subjects and by coding and limiting access to data. Each participant will be assigned a research subject number. The only documents linking the

subject's identity with her subject number will be the consent form and the enrollment log. The contact information list and payment request forms will contain the subject's identity only. The medical questionnaire, pregnancy test result, and data spreadsheets will reference the subject number only. The subject's social security number, required on the payment request form, will be blacked out once payment has been processed. Once the study is complete, all contact information will be deleted, unless the participant requests to be contacted for future studies conducted by [name] or his colleagues. All of the participant's study documents will be kept in a locked file cabinet in the study coordinator's office. Databases containing PHI will be maintained on a password-protected computer with full disk encryption.

### ***Coercion***

Coercion occurs when potential participants feel compelled to participate in research for reasons such as perceived demand or the availability of large sums of reimbursement. This can be particularly true when there is little benefit to the individual for their participation. In this study, there is minimal risk of coercion as personnel will inform subjects of their rights as a research participant, including their right to refuse to participate or to withdraw from the study at any time without penalty. Reimbursement (\$50) is not believed to be coercive, based on the time required and the nature of the research. The amount of reimbursement is comparable to similar studies.

### ***Discomfort with the Nature of the Research***

Participants may feel discomfort with the personal nature of this research. Before the participant is enrolled in the study, detailed study procedures will be explained so she is aware of what the research entails. Subjects will provide personal information, such as sexual health and history. Some study procedures will be conducted with the physician/nurse and research assistant/chaperone in the room, including insertion of the mLCI device into the vagina by the physician/nurse (similar to a pelvic exam) and making measurements with the device. Participating in these research procedures and providing personal information may be uncomfortable for some women. It is unlikely this discomfort will result in any serious adverse events. Should participants report discomfort with the research, they will be reminded of their rights to not participate in the study or to withdraw from the study at any time. Subjects may contact the principal investigator or one of the study physicians at any time to discuss questions or concerns about the study.

### ***Side Effects from Study Procedures and/or Devices***

Risks of the mLCI Device: The mLCI device will be handled gently for placement against cervical tissue. We expect very minimal risk for tissue abrasion or irritation as the devices will have a smooth plastic and silicone surface and commercial gynecological lubricant will be applied before cervical contact. The device will be cleaned in full accordance with high level disinfection clinical procedures at DUHS. Specifically, probes will be enclosed in a Trophon EPR high-level disinfection system to disinfect all external surfaces. Study staff will complete training and competency reviews per institutional procedures. For the mLCI technique, a fiber optic bundle transmits near infrared light onto the epithelia to image the cervix. The light source has been either certified for medical use or tested to demonstrate that it complies with medical safety standards.

### **Costs to the Subject at Duke**

There will be no costs to the subject as a result of participating in this study.

## **Data Analysis & Statistical Considerations**

### ***Data analysis for Duke site***

The proposed study is designed as a pilot study, intended to provide feasibility and usability data to inform future studies on a larger scale. The planned pilot study will include 10 subjects, which will yield success/failure metrics of the probe design with 10% precision. Elements of the probe performance that will be evaluated include ease of use by the medical practitioner, patient comfort, ability to access the relevant anatomy, and quality of mLCI imaging data. Because the goal of the pilot study is the evaluation of general feasibility, no subject data will be excluded if no predetermined exclusion criteria are met.

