### **Multi-site Study: Responsibilities**

[name], the Duke PI of this study, is the primary awardee of the NIH grant supporting this work. [name] and his team have developed the mLCI research device and will conduct a small study at Duke (described below) to assess if any adjustments to the device are needed before it is sent to Jacobi Medical Center for the larger study. The study at Jacobi Medical Center will be funded as a subaward / consortium agreement of [name] NIH grant. The research proposed in this study protocol addresses Specific Aim 1 of the NIH grant.

Duke will recruit up to 15 women to enroll in this study, in order to achieve the target number of 10 subjects who complete the study at that site. Jacobi will enroll up to 100 women for this study, in order to achieve the target number of 40 women who complete the study at that site. Data from both sites will be analyzed at Duke. Data received from Jacobi will be de-identified before being sent to Duke. Study conduct at Duke will be under the oversight of the IRB of the Duke University Health System. Study conduct at Jacobi Medical Center will be under the oversight of the IRB of the Albert Einstein College of Medicine and Montefiore Medical Center.

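### The 10% precision claimed for 10 Duke subjects is undefined and fails as a 95% margin: exact half-widths run from 15.4 to 31.3 percentage points

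*Combined protocol and SAP*

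**What the plan says.** The section *Data analysis for Duke site* describes a feasibility and usability pilot and states: "The planned pilot study will include 10 subjects, which will yield success/failure metrics of the probe design with 10% precision". The elements to be evaluated are "ease of use by the medical practitioner, patient comfort, ability to access the relevant anatomy, and quality of mLCI imaging data".

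*Multi-site Study: Responsibilities* gives the same target, 10 completers from up to 15 enrolled. It says that the Duke study is run "to assess if any adjustments to the device are needed before it is sent to Jacobi Medical Center for the larger study".

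No section defines precision or gives a confidence level, an interval method or an expected success rate for Duke. *Data analysis for Jacobi site* also uses a figure of 10%, but for a different quantity: the average absolute difference between two estimates of epithelial area.

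**The concern.** The phrase "with 10% precision" is the only statistical support offered for the Duke sample size. In a section on statistical considerations, most readers would take it as a margin of error of plus or minus 10 percentage points, usually at 95% confidence. Ten binary outcomes cannot deliver that.

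What is at stake is how the pilot is read. Its results inform possible changes to the device before the larger study, and the planning of later studies. If 9 of 10 placements succeed, a reader relying on the stated precision would take the true rate to be about 80% or more (90 minus 10). The data would not rule out a rate near 55%.

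**Working it through.** **Inputs.** From the plan: n = 10, a success/failure metric in one group, and a stated precision of 10%. Not in the plan, so assumed: a two-sided 95% level, the exact Clopper-Pearson interval, and every possible result from 0/10 to 10/10. Other levels and methods follow as a sensitivity check.

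**Can the plan's 10% be reproduced?** Two readings come out at or near 10%:

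- Step size of the observed proportion: 1/n = 1/10 = 10 points, an exact match.
- One standard error, √(p(1−p)/n). At p = 0.9, √(0.9 × 0.1/10) = 0.095, or 9.5 points. At p = 0.8 it is 12.6 and at p = 0.5 it is 15.8, so this reading needs an unstated true rate near 90%.

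It is not reproduced as a 95% confidence margin.

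**Exact 95% intervals.** For x successes in n, the lower limit is the 0.025 quantile of Beta(x, n−x+1) and the upper limit is the 0.975 quantile of Beta(x+1, n−x). The lower limit is 0 at x = 0 and the upper limit is 1 at x = n. At x = n the lower limit reduces to 0.025^(1/n). For 10/10 this is 0.025^(1/10) = 0.6915, so the half-width is (1 − 0.6915)/2 = 0.154.

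| Result | Exact 95% interval | Half-width (points) | Below estimate | Above estimate |
|---|---|---|---|---|
| 10/10 | 69.2–100% | 15.4 | 30.8 | 0 |
| 9/10 | 55.5–99.7% | 22.1 | 34.5 | 9.7 |
| 8/10 | 44.4–97.5% | 26.5 | 35.6 | 17.5 |
| 7/10 | 34.8–93.3% | 29.3 | 35.2 | 23.3 |
| 6/10 | 26.2–87.8% | 30.8 | 33.8 | 27.8 |
| 5/10 | 18.7–81.3% | 31.3 | 31.3 | 31.3 |

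Results from 0/10 to 4/10 mirror these. The smallest half-width is 15.4 points. Half-width is also a lenient measure near the extremes: at 10/10 the whole interval lies below the estimate and reaches 30.8 points down.

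**Other methods at 95%.** Half-widths are 13.9 to 26.3 points (Wilson), 16.0 to 26.3 (Agresti-Coull) and 10.9 to 27.6 (Jeffreys). The Wald interval falls to 10 or less only at 0/10 and 10/10, where its width collapses to zero. That is an artefact of the formula.

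**Lower confidence levels.** The smallest exact half-width, at 10/10, is (1 − 0.05^(1/10))/2 = 12.9 points at 90% confidence and (1 − 0.10^(1/10))/2 = 10.3 at 80%. Some approximate methods do go below 10 at these levels, but only when every subject succeeds or every subject fails (Jeffreys at 90%: 8.5; Wilson at 80%: 7.1). At 9/10 the same two intervals are 15.6 and 12.6.

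**More subjects.** If all 15 permitted enrollees completed and all succeeded, the exact 95% half-width would still be (1 − 0.025^(1/15))/2 = 10.9 points. It first drops below 10 at 17 out of 17 (9.8 points). For a half-width of 10 points or less at other success rates, the exact method needs about 46 subjects at 90%, 70 at 80% and 104 at 50%. These numbers show the scale of the gap; they are not a proposal to enlarge the pilot.

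**The case against.** The strongest reply is that the plan never mentions a confidence interval, so the 95% benchmark is brought in from outside. With 10 subjects an observed proportion moves in steps of exactly 10%, and the authors may have meant no more than that. On this reading the arithmetic is right and only the word is loose. That the term is undefined is certain; that the figure is wrong depends on how the term is read. This stands as a limit on the claim. It does not save the sentence, because step size is the resolution of an observed proportion and says nothing about how far that proportion may lie from the truth.

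A second reply is that little depends on it. The pilot has no hypothesis test, no go/no-go rule on a Duke proportion, and no later sample size derived from the 10%. Device changes can follow from individual failures of access, comfort or image quality, which needs no narrow interval. This also stands, and it keeps the weight modest. It justifies a small sample without a power calculation. It does not justify a numerical precision claim that the sample cannot support.

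A third reply is that success is not defined for any of the four evaluated elements, nor is it stated whether it is counted per subject or per insertion attempt. That is true, and these definitions are needed before any interval can be computed. It is a separate gap and does not make the precision statement right.

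**Conclusion.** The concern holds. The precision statement is undefined, and as a 95% margin of error it is not met at any possible result: exact half-widths run from 15.4 to 31.3 points, about 1.5 to 3 times the stated figure. The size rests on a two-sided 95% level and the exact method, neither of which the plan specifies. Wilson, Agresti-Coull and Jeffreys intervals at 95% lead to the same conclusion, as does the exact interval at 90% and 80%. The sentence should be corrected because it is the only statistical basis given for the Duke sample size. The pilot's aim and its 10 subjects are not called into question.

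**What to change.** Replace the precision claim with a statement of what 10 subjects provide, for example:

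> With 10 subjects, the exact 95% confidence interval is 69.2–100% for 10/10 successes, 55.5–99.7% for 9/10, 44.4–97.5% for 8/10 and 18.7–81.3% for 5/10.

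Add that each Duke success/failure metric will be reported with its exact 95% interval. If the authors meant only the step size of the observed proportion, they should say so and not call it precision.

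The cost is one sentence plus the reporting commitment, and a less favourable figure on the page. Sample size, feasibility aim and study procedures do not change.

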### **Design & Procedures**

#### **mLCI instrument**

The purpose of this instrument is to obtain optical measurements from the cervix via a vaginal probe to create a map of the surface cells that distinguishes the ectocervical and endocervical epithelia. The boundary between the two cell types is known as the squamocolumnar junction, or “t-zone”, which is the transitional region at which cervical dysplasia is most likely to occur.

The instrument delivers infrared light to 36 locations on the cervix, and measures the depth-profile of back-scattered light from each location using low coherence interferometry (LCI). This technique is thus termed multiplexed LCI (mLCI). The LCI profile data is stored by a computer for subsequent analysis to identify cell type.

The components of the mLCI instrument are grouped in the following modules: 1) Optical probe, 2) mLCI interferometer, 3) white light imaging module, 4) computer, and 5) physical enclosure.

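### The Duke plan quantifies only success/failure in 10 women and defines no graded or within-woman summary, although stored channel profiles and paired placements would support one

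*Combined protocol and SAP*

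**What the plan says.** The section on data analysis for the Duke site is one paragraph. Its single quantified statement is: "The planned pilot study will include 10 subjects, which will yield success/failure metrics of the probe design", with a stated precision of 10%. It then lists what will be evaluated: "ease of use by the medical practitioner, patient comfort, ability to access the relevant anatomy, and quality of mLCI imaging data". No scale, threshold, summary statistic or interval is given for any of these four elements, and no method is given for comparing two placements in the same woman.

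The description of the instrument says what each acquisition produces: "The instrument delivers infrared light to 36 locations on the cervix, and measures the depth-profile of back-scattered light from each location". It adds: "The LCI profile data is stored by a computer for subsequent analysis to identify cell type". Channel-by-channel reading is specified in the Jacobi analysis section but not for Duke.

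The Duke study procedures plan two placements per woman, first without and then with a speculum, and an optional third with an alternate speculum. On placement time they say: "Up to 4 minutes will be allotted for probe manipulation for optimal contact". Table 1 repeats this as a maximum. Neither place says that elapsed time is recorded, and the procedures allow an attempt to end because the time has run out. The text after Table 1 says that comparing measurements with and without a speculum will show whether camera guidance is enough. The section on multi-site responsibilities says that the Duke study is to assess whether the device needs adjusting before it goes to Jacobi.

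**The concern.** The Duke part has two jobs: to show whether and what to adjust before the device is shipped, and to compare two ways of inserting the probe in the same women. The one output that the plan quantifies suits neither with 10 women. A yes/no result does not say whether a failed or marginal image lost 3 channels or 30, and it does not separate a quick placement from one that barely met the limit. As a paired comparison, yes/no results use only the women whose two placements disagree.

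The material for something better is largely in the design. Profiles are stored by channel, each woman is her own control, and a clock must already be watched to enforce the limit. If no graded measure or readability criterion is fixed beforehand, image quality will be judged after the data are seen, and the speculum question will rest on a handful of discordant pairs.

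**Working it through.** **Inputs from the documents.** 10 women completing at Duke (data analysis for Duke site; multi-site responsibilities); 36 channels (mLCI instrument); a 4-minute placement limit, 4 x 60 = 240 s, and two planned placements per woman (Duke procedures, Table 1). **Assumed:** the SD of channel counts, shown as a range because the documents give none.

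**1. The plan's own figure.** The step between possible results is 1/10 = 10 points. The standard error at a true rate of 90% is sqrt(0.9 x 0.1/10) = 9.5 points. The 95% Wald half-width, 1.96 x sqrt(p(1-p)/10), is 31.0 points at p = 50%, 24.8 at 80% and 18.6 at 90%. Exact 95% intervals are 55.5% to 99.7% for 9/10 and 69.2% to 100% for 10/10. So the stated 10% matches the step size, or roughly one standard error at a high success rate, but not a 95% half-width at these rates.

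**2. Paired yes/no results, 10 women.** Exact two-sided p when all d discordant pairs agree is 2 x 0.5^d.
- d = 5: 0.0625. d = 6: 0.031.
- Six discordant pairs is therefore the minimum, and all six must point one way. One dissenting pair is tolerable only with 9 or 10 discordant pairs: 2 x (1 + 9)/512 = 0.039 for 8 against 1, and 2 x (1 + 10)/1024 = 0.021 for 9 against 1.
- In the most favourable case, where every discordance goes the same way, power is P(Bin(10, p) >= 6). This is 0.80 at p = 0.673, so the true difference must be about 67 points. At 50 points power is 38%, and at 30 points 5%.

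**3. Readable channels per woman, no time-outs.** One count per woman, so n = 10 and correlation between channels does not enter. The half-width for the mean is t(0.975, 9) x SD/sqrt(10) = 0.715 x SD.

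| SD (channels) | SD (points of 36) | 95% half-width (points) |
|---|---|---|
| 3 | 8.3 | 6.0 |
| 5 | 13.9 | 9.9 |
| 7 | 19.4 | 13.9 |

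For the within-woman difference, a paired t-test with 10 women has 80% power at a mean difference of 1.0 SD of the differences. A signed-rank test has about 78% if the differences are normal. With an SD of 5 channels, that is 5 channels, or 5/36 = 14 points.

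**4. Time-outs averaged in as zeros.** Nine women at 34 channels and one at 0: SD = 34 x sqrt(0.9 x 0.1 x 10/9) = 10.8 channels = 29.9 points, so the half-width is 0.715 x 29.9 = 21.4 points. The Wald half-width for 9/10 is 18.6. Two time-outs: SD = 34 x sqrt(0.8 x 0.2 x 10/9) = 14.3 channels, half-width 28.5 points, against 24.8 for 8/10. With zeros mixed in, the graded mean is no tighter than the proportion.

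**The case against.** A reader might infer that the plan reduces all Duke performance to yes/no and throws away most of what 10 women can tell. The documents do not support that.
- Success/failure is the only quantified output, but the next sentence lists image quality and three other elements with the scale left open.
- Profiles are stored, and the section says that no subject data will be excluded unless predetermined criteria are met. Nothing is shown to be discarded.
- The 4 minutes is a ceiling, not a recorded duration, so placement time is not already in hand.
- An attempt can end at the limit without a set of 36 readings.
- The share of information lost cannot be derived. If the 360 readings from one placement per woman were pooled, the effective number would be 360/(1 + 35 x ICC). This exceeds 20, twice the number of women, only if the ICC is below 17/35 = 0.49, and no ICC is given. For placement time, if roughly normal, cutting to yes/no loses 36% of the information on the mean at a 50% success rate and 66% at 90%.

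Two further objections have weight. This is a feasibility pilot with no stated hypothesis, alpha or power, so the test in step 2 is a yardstick for how little paired yes/no data can show, not a standard that the plan set. And whether camera guidance is sufficient is partly a placement success question, so success/failure should stay. Comfort and access to the anatomy gain nothing from channel counts.

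What remains is that no graded or paired summary is defined for a comparison that the plan says it wants.

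**Conclusion.** The point holds as an omission. The Duke section quantifies only success/failure, and defines neither a graded measure nor a within-woman analysis. On yes/no data alone, the speculum comparison needs a true difference of about 67 points for 80% power, even if all discordance runs one way. A per-woman channel count could detect a mean difference of about 1.0 SD and give a mean share to within 6.0 to 13.9 points for an SD of 3 to 7 channels.

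That gain is conditional. It rests on an SD that the documents do not give, on roughly normal counts, and on no placement timing out. Averaging time-outs in as zeros removes it, so placement success and channel yield must be reported as two measures. The half-widths are for a mean; for roughly normal counts, an interval for a median would be somewhat wider.

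**What to change.** In the Duke analysis section:
1. Keep placement success/failure per insertion method, with an exact 95% interval in place of the 10% precision statement.
2. Add, with the woman as the unit, readable channels out of 36 among placements that reached contact, using a per-channel readability threshold set before data are seen.
3. Add recorded seconds to contact, with time-outs treated as censored at 240 s.
4. Report medians with 95% intervals per method, and the within-woman difference by a rank-based paired method in which a time-out ranks worst.
5. State which speculum attempt enters the pair, since a third attempt is optional. Note that the order of placements is fixed, so the paired difference includes any order effect.

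The cost is a readability threshold agreed in advance, a time entry on the form and some analysis wording. No extra women, visits or procedures are needed.
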